Investigation Number: QS-IS-G-H-2201

ClinicalTrials.gov ID: NCT05651867

CIV-ID: 2022-A01812-41

Document title: EGLE Clinical Investigation Synopsis

Doc No: CA-LU-SYN-020-(EN)

Revision: A

CLINICAL INVESTIGATION SYNOPSIS

EGLE study

Prospective clinical investigation on the evaluation of performance and safety of the EPIONE assisted CT-guided percutaneous procedures in the lungs

Clinical investigation plan: CA-LU-CIP-0019-Rev3

Effective date

26-May-2025

Author name

[name]

Sponsor

Quantum Surgical SAS
[name]
[name]
FRANCE

Entity funding the study

Quantum Surgical SAS

Investigation Number: QS-IS-G-H-2201

ClinicalTrials.gov ID: NCT05651867

CIV-ID: 2022-A01812-41

Document title: EGLE Clinical Investigation Synopsis

Doc No: CA-LU-SYN-020-(EN)

Revision: A

Revision History

Rev.	Description	Date	Author
A	Creation of the document in English from CA-LU-CIP-0019-Rev3	26-May-2025	[name]

Signatures

Role	Name	Date	Signature
Clinical Project Leader	[name]	26-May-2025	Signed on DocuSign
Clinical representative	[name]	26-May-2025	Signed on DocuSign

Investigation Number: QS-IS-G-H-2201

ClinicalTrials.gov ID: NCT05651867

CIV-ID: 2022-A01812-41

Document title: EGLE Clinical Investigation Synopsis

Doc No: CA-LU-SYN-020-(EN)

Revision: A

Full study title	Prospective clinical investigation on the evaluation of performance and safety of the EPIONE assisted CT-guided percutaneous procedures in the lungs
Brief study title	EGLE study
Study design	Clinical investigation of a CE marked device, used outside of its current indication, for an extension of the indication to the lungs. Interventional, prospective, non-randomized, non-comparative, single arm study
Study category	Category 1 according to ANSM categorization
Study centres	Gustave Roussy Cancer Center Therapeutic Imaging Department [name] FRANCE
Purpose of the clinical investigation	The Epione device is a robotic device that assists the physician during CT-guided percutaneous treatment. This device is validated in clinical practice for abdomen. The aim of this clinical investigation is to confirm in patients the accuracy and safety of the Epione device designed to assist radiologists during percutaneous procedures the lungs and thus, extend the Epione indication.
Primary objective and endpoint	Primary objective: Evaluation of the feasibility of the EPIONE device in assisting needles insertion in CT-guided intervention in the lungs. Primary endpoint: The primary feasibility endpoint is the technical success of the intervention per lesion.
Secondary objectives and endpoints	Secondary objectives: Evaluation of safety and performance parameters Secondary criteria: Safety 
Adverse Event(s) (AE): all AEs (serious and non-serious, including deficiency or dysfunction) and AEs related to the device or the intervention. Performance 
Assessment of the needle placement accuracy through an estimation of the distance from the needle inserted and the predefined planning;Assessment of the number and the grade of needle adjustments to achieve technical success;Assessment of post-intervention ablation success (ablation only);Assessment of local tumor progression.
Eligibility criteria	Inclusion criteria 
Patient ≥ 18 years,Patient for whom a percutaneous CT-guided intervention in lung has been prescribed and agreed by a multidisciplinary team of radiologists, surgeons and clinicians,Patient with a signed informed consent form.Patient covered by a social security system.

Investigation Number: QS-IS-G-H-2201

ClinicalTrials.gov ID: NCT05651867

CIV-ID: 2022-A01812-41

Document title: EGLE Clinical Investigation Synopsis

Doc No: CA-LU-SYN-020-(EN)

Revision: A

	
Exclusion criteria
 
• Patient unable to undergo general anesthesia,• Pregnant or nursing female, confirmed before the intervention• Patient already participating in another clinical study
Device and comparator	
The Epione investigational device is a user controlled, stereotactic accessory intended to assist in the planning and manual advancement of one or more instruments, as well as in verification of instrument position during Computed Tomography (CT) guided percutaneous procedures.
 
The Epione device is composed of 3 main components (Robot cart, Display cart with software and Navigation cart) and 3 instruments (Introducer guide, Patient reference and Navigation probe).
 
There is no comparator.

Procedures to use the device	
The operating principle of the subject device is the following:
 
• pre-interventional CT-scan acquisition• planning with the device's software (choice of the needle's trajectory to reach the targeted point)• needle's insertion according to the predefined planning• acquisition of an per-intervention CT-scan to evaluate the needle(s) placement.
Study flowchart	
Schematic diagram of visit schedule:
 
The diagram illustrates the visit schedule with five vertical dashed lines representing time points. An orange arrow points from left to right, indicating the progression of time. The visits are labeled as follows:
 
Visit 1: $(D_0 - 1m) \leq D \leq D_0$. Description: Routine pre-intervention consultation.Visit 2: D_0. Description: Day of the intervention.Visit 3: $D_0 + 2w \leq D \leq D_0 + 6w$. Description: Routine follow-up visit at 1M.Visit 4: $D_0 + 4m \leq D \leq D_0 + 8m$. Description: Routine follow-up visit at 6M.Visit 5: $D_0 + 10m \leq D \leq D_0 + 14m$. Description: Routine follow-up Visit at 12M. 
• Visit 1: initial visit – patient screening ($D_0-1 \text{ month} \leq D \leq D_0$)
 
Prior to the intervention, interventional radiologists perform a pre-intervention consultation with the patient. During the consultation, a review of inclusion and exclusion criteria is performed, presentation of the study and the device (oral and printed information for the patient). Paper information notice and informed consent forms are read and given to the patient with sufficient time to consider the study's implications before deciding whether to participate. Next visit planned (day of the CT-guided intervention).
 
• Visit 2: inclusion visit –Day of the intervention D_0
 
Retrieval of the signed informed consent form by the investigator (signed by the patient and the investigator), confirmation of enrollment and validation of screening (inclusion and non-inclusion criteria are confirmed), demographic data, tumor data, primary cancer data as well as other medical history. Collection of concomitant pathologies/treatments.

Investigation Number: QS-IS-G-H-2201

ClinicalTrials.gov ID: NCT05651867

CIV-ID: 2022-A01812-41

Document title: EGLE Clinical Investigation Synopsis

Doc No: CA-LU-SYN-020-(EN)

Revision: A

Patient placed under general anesthesia. Acquisition of the pre-intervention CT-guided image of the lungs. Confirmation of the prescribed CT-guided intervention realization (if the intervention is not maintained, the patient's exit from the study, for screening failure). Planning with the subject device to visualize the path of needle(s) to the target. Planning validation by the investigator and then insertion of the needle(s) to the targeted area with the subject device. Acquisition of the per-intervention image under CT guidance. Validation of the correct positioning of the needle(s). Completion of the CT-guided intervention with a needle routinely used by the investigator. Acquisition of the post-intervention CT-guided image and evaluation of possible adverse events. In case of interventions on multiple lesions, the absence of a non-reduced major pneumothorax must be confirmed to use the device again for the next intervention. In case of interventions performed on different days on or both lungs treated on two different days, the additional intervention day will be added to the D0 sheet.

- Visit 3: post-intervention follow-up visit at 1 month (D0+2 weeks ≤ D ≤ D0+6 weeks)**

Follow-up of AEs related to the intervention and record of possible new AE/SAEs.

Review of the acquired image (CT-scan or equivalent) of the lungs to evaluate for ablation the ablation site local tumor progression and establish a baseline situation of the treated tumor.

- Visit 4: post-intervention follow-up visit at 6 months (D0+4 months ≤ D ≤ D0+8 months)**

Review of the acquired image (CT-scan or equivalent) of the lungs to evaluate ablation site local tumor progression and evaluation of possible AE/SAEs.

- Visit 5: post-intervention follow-up visit at 12 months (D0+10 months ≤ D ≤ D0+14 months)**

Review of the acquired image (CT-scan or equivalent) of the lungs to evaluate ablation site, local tumor progression and evaluation of possible AE/SAEs.

Sample size	25 patients
Randomisation and blinding	Not applicable.
Statistical analysis method	The statistical analysis will be performed by an external CRO (Delta Data Consultants, Eybens, France). All statistical analyses will be produced using SAS® 9.4 software (Cary, NC, USA)..
Study duration per patient	From patient's informed consent form signature to visit 5. From 10 months to 15 months, depending on the day of patient's signed informed consent retrieval and the day of the visit 5: 
10 months if the patient informed consent form is collected the day of the intervention, and the last visit is performed at the beginning of the time window (10 months)15 months if the patient informed consent form is collected at the initial visit 1 month before the intervention, and the last visit performed at the end of the time window (15 months)
Study schedule	Planned start: October 2022 Planned recruitment time: 6 months Planned last patient out: Q1 2024

1. ABBREVIATIONS

ANSM	L'Agence nationale de sécurité du médicament et des produits de santé
ADE	Adverse Device Effect
AE	Adverse Event
CE	European Conformity
CRF	Case Report Form
CSR	Clinical Study Report
CT	Computed Tomography
DRM	Data Review Meeting
eCRF	electronic Case Report Form
GGO	Ground Glass Opacity
ITT	Intention to Treat
LTP	Local Tumor Progression
MAM	Minimal Ablation Margin
NSCLC	Non-Small Cell Lung Cancer
PP	Per Protocol
PMCF	Post Market Clinical Follow-up
PT	Preferred Term
SAE	Serious Adverse Event
SADE	Serious Adverse Device Effect
SAP	Statistical Analysis Plan
SIR	Society Interventional Radiology
SOC	System Organ Class
SOP	Standard Operating Procedure
TNM	Tumor Nodule Metastasis

2. INTRODUCTION

The purpose of the Statistical Analysis Plan (SAP) is to describe:

- The statistical methodology.
- The calculated/derived variables.
- The general rules and conventions.
- The tables and listings to be included in the Clinical Investigation Report (CIR).

The SAP is based on the Clinical Investigation Plan version 2.0 dated 9th September 2022 and the Case Report Form (CRF) version 2.0 dated 31st March 2023.

3. CLINICAL INVESTIGATION PLAN SUMMARY

The following definitions concern the study:

Designation	Definition
Needle tip	The distal extremity of the inserted needle (sharp end)
Target	The point in the scanner aimed at during the intervention; the point where the operator decides to place the needle tip during the planning phase
Adjustment	A manipulation of the needle by the operator after the insertion phase guided by the EPIONE® device in order to obtain an acceptable trajectory to continue the intervention. This does not include the manipulation of a needle initially and voluntarily planned and/or inserted at a distance from the target by the operator. The adjustment can be: MINOR : Adjustment in depth, in the axis of the needle (advance or retrieve). MEDIUM : Lateral adjustment, the needle does not entirely leave the patient's body. MAJOR : Total removal of the needle(s) from the patient's body and reinsertion of the needle following the same planned trajectory, or a new trajectory to reach the target.

3.1. Study objectives

Primary objective:

The primary objective of the study is to demonstrate the **feasibility of the Epione® device** in assisting needle insertion in CT-guided intervention in the lungs.

The primary endpoint to feasibility is the technical success of the intervention per lesion assessed from **the percentage of robotically assisted lesion targeting and needle placements that were accurate enough to allow the percutaneous intervention.**

The technical success of the intervention will be described by lesion with a Boolean, YES or NO answer to the question:

“Is/are the needles positioned accurately enough to allow next step of the intervention?”.

Secondary objectives:

The secondary performance objectives are the following:

- Assessment of the needle placement accuracy.
- Assessment of the number and grading of needle adjustments.
- Assessment of immediate post-intervention ablation success (ablation only).
- Assessment of the long-term performance of ablation: local tumor progression (LTP) rate (ablation only).

The secondary safety objectives are the following:

The safety assessment is based on the reporting of all AEs (serious and non-serious, including deficiency or dysfunction) and AEs related to device or intervention (see Clinical Investigational Plan Section 8 for definition and recording/reporting modalities including severity and causality SIR classification).

3.2. Study design

3.2.1. Study design and device

This is an interventional, prospective, non-comparative, non-randomized and single-arm study of a CE marked device, used outside of its intended use according to the Medical Devices Regulation MDR (EU) 2017/745.

The Epione® device is a Class IIa, non-invasive device and, as such, falls into Case #1 of the ANSM categorization (pre-market study category 1).

Eligible patients scheduled for an Epione® CT-guided intervention in the lung from the investigator's site will be proposed to participate. If they agree, they are enrolled. In case

the prescribed intervention is not maintained, the patient will be removed from the study without any impact on the inclusion window.

The inclusion period (recruitment) is estimated as 6 months for 25 patients (*i.e.* at least 25 CT-guided interventions in the lungs: at least 1 per patient). The inclusion rate will depend on the number of sites using the Epione® device routinely. Two study sites in France are expected to participate in this clinical investigation, Gustave Roussy (Villejuif) will be the coordinating center and a second site will be the Hôpital de La Timone (Marseille).

Considering the main criteria is feasibility, a technical failure of the whole intervention (for all the lesions planned in case of multiple lesions) leads to patient's premature end of study and study withdrawal. In this case, the only data available and analysable will be the technical success of lesion treatment (primary endpoint).

The study device is a user-controlled, stereotactic accessory intended to assist in the planning and manual advancement of the needle, as well as aiding the verification of needle position during CT-guided percutaneous ablation procedures.

The operating principle of the investigational device is detailed in section 6.2 of the protocol.

Five visits will be recorded in the CRF.

- **Visit 1** (within one month before treatment): the first visit is planned to screen the patient, present the study, and deliver the information notice and informed consent form.
- **Visit 2** (treatment): the second visit consists of recovery of the signed informed consent form, confirmation of enrolment, validation of screening, and collection of demographic and tumor characteristics. Pre-intervention CT-guided image, planning of needle trajectory and insertion of needle into targeted area using study device, per-intervention CT-guided image and post-intervention CT-guided image will all be performed.
- **Visit 3:** Follow-up at 1 month (between 2 weeks and 6 weeks after treatment).
- **Visit 4:** Follow-up at 6 months (between 4 months and 8 months after treatment).
- **Visit 5:** Follow-up at 12 months (between 10 months and 14 months after treatment), end of study.

See Section 9 of the Clinical Investigation Plan for a detailed description of each visit.

Technical success is defined as:

When the needle(s) tip(s) reach(es) the target(s) with sufficient accuracy to pursue the intervention, and:

- Robotic needle insertion is performed without adjustment.

- Robotic insertion with only minor or medium adjustment(s).
- Robotic insertion is performed with one robotic major adjustment.

Technical failure is defined as:

When the needle tip does not reach the target with sufficient accuracy to pursue the intervention:

- If insertion of one or several needle(s) from the skin is fully manual.
- Failure of a robotic major adjustment.
- Note: if a lesion cannot be treated because of a major pneumothorax on the previous lesions treated, the lesion is excluded from the study and is not taken into account in feasibility statistics.

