4.2. Changes in the planned analyses

Any major/minor changes from the SAP will be discussed in the study report.

Definitions of the Per Protocol population and the Safety Population have been slightly modified from the definition in the protocol, indeed it has been clarified by the Sponsor that treated patients include all patients with an assistance of at least one needle placement with EPIONE®, even if the procedure (ablation, biopsy, fiducial placement or abscess drainage) was not performed using the EPIONE® device in accordance with protocol specifications.

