5.3. Analysis populations

Four different analysis populations are foreseen:

Screened Population

All patients who are proposed to enter the study.

Intention-to-Treat (ITT) Population

All screened patients who have confirmed their signed informed consent and are planned to be treated using the Epione® device.

Per Protocol (PP) Population

All patients in the ITT population treated by the Epione® device, including those for which the procedure was not completed with the Epione® device, without any major deviation.

Safety Population

All patients in the ITT population treated by the Epione® device, including those for which the procedure was not completed with the Epione® device.

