5.5.4. Handling of dropouts and missing data

Missing data will not be imputed, except dates (missing day) if needed in order to calculate durations.

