6. STUDY PATIENTS

6.1. Disposition of patients

The disposition of patients according to populations of analysis (Screened, ITT, PP, Safety) and visits (Visit 1 – Screening, Visit 2 – Intervention, Visit 3 – Follow up at 1 month, Visit 4 – Follow-up at 6 months and Visit 5 – Follow-up at 12 months, End of study) will be presented using frequency and percentages.

End of study information (normal end of follow-up (Visit 5 performed), AEs, screen failures, patient's will to withdraw from study, lost to follow-up, device deficiency or dysfunction, death and other) will be presented using frequency and percentages.

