10. SAFETY ANALYSES

The secondary safety analysis will be conducted on the Safety population.

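### SAP 3.2.1 withdraws whole-intervention technical failures with no exception for safety data, so their later AEs may go unrecorded while they still count in the AE percentages

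*SAP*

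**What the plan says.** - **Withdrawal.** SAP 3.2.1 says that a technical failure of the whole intervention (all planned lesions, if there are several) leads to "premature end of study and study withdrawal". It continues: "In this case, the only data available and analysable will be the technical success of lesion treatment (primary endpoint". Safety data are not exempted.
- **Safety population.** SAP 5.3 takes ITT patients treated by the device, "including those for which the procedure was not completed with the Epione® device". The one-needle criterion is in SAP 4.2: "treated patients include all patients with an assistance of at least one needle placement with EPIONE".
- **Safety analysis.** SAP 10: "The secondary safety analysis will be conducted on the Safety population". SAP 10.1.1 has AEs reported throughout the study and summarised as numbers of events and as numbers and percentages of patients, with no allowance for length of follow-up.
- **Planned AE follow-up.** In the protocol synopsis (Study flowchart row), Visit 3, at 2 to 6 weeks, includes: "Follow-up of AEs related to the intervention and record of possible new AE/SAEs". AEs are reviewed again at 6 and 12 months.
- **Missing data.** SAP 5.5.4: "Missing data will not be imputed, except dates (missing day) if needed in order to calculate durations".
- **End-of-study reasons.** SAP 6.1 ends its list with "lost to follow-up, device deficiency or dysfunction, death and other". Technical failure is not named.

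**The concern.** The withdrawal rule and the Safety population pull in opposite directions. One takes a patient out of the study on the intervention day; the other keeps that patient in the denominator of every AE percentage. If AE recording stops at withdrawal, the patient can appear as event-free for a period in which the study recorded nothing.

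The loss would not be random, because these patients are selected by device failure. The synopsis gives confirmation of accuracy and safety in the lungs as the purpose of the study, with a view to extending the indication. Events that appear some days after a failed robotic insertion are part of that question.

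**Working it through.** The plan has no figure of its own to reproduce here. The sample size rests on recruitment (SAP 3.4), and no AE rate, failure rate or safety threshold is given. The check is therefore a reading of the rules followed by an illustration.

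**1. Can one patient fall under both rules?** Yes. SAP 3 defines an adjustment as something done after the device-guided insertion, and SAP 9.1.1 counts a failed robotic major adjustment as technical failure. A patient whose only lesion fails in this way has had an assisted needle placement, so is in the Safety population, and is also withdrawn. A patient whose needles were all inserted manually, with no device assistance, is outside the Safety population.

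**2. Which AEs are exposed?** Those after the intervention day. Intervention-day AEs are probably kept: the synopsis evaluates possible AEs at Visit 2, and SAP Table 4.1 covers AEs during the intervention. Visits 3 to 5 come after the withdrawal.

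**3. Direction.** Let x be the patients with a recorded AE and m the patients whose only AE is an unrecorded later one. The table shows x/25; full recording would show (x + m)/25. Since m cannot be negative, the percentage can only be too low.

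**4. Expected shortfall.** Inputs: 25 Safety patients (the target, taken as the denominator); f = Safety patients withdrawn for whole-intervention failure; q = chance that such a patient has a first event after the day. Both f and q are assumptions. Shortfall = f × q / 25, in percentage points:

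| f | q = 5% | q = 10% | q = 20% |
|---|---|---|---|
| 0 | 0 | 0 | 0 |
| 1 | 0.2 | 0.4 | 0.8 |
| 2 | 0.4 | 0.8 | 1.6 |
| 3 | 0.6 | 1.2 | 2.4 |

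The chance that at least one such patient's event is missed is 1 − (1 − q)^f. It is 5% for f = 1, q = 5%, and 1 − 0.8³ = 49% for f = 3, q = 20%.

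**5. Bounds.** Suppose 2 patients have a recorded AE (assumed), and withdrawn patients are counted first as event-free and then as having an event. Exact (Clopper-Pearson) 95% CIs:

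| Withdrawn patients counted as events | Rate | 95% CI |
|---|---|---|
| 0 | 2/25 = 8.0% | 1.0 to 26.0 |
| 1 | 3/25 = 12.0% | 2.5 to 31.2 |
| 2 | 4/25 = 16.0% | 4.5 to 36.1 |
| 3 | 5/25 = 20.0% | 6.8 to 40.7 |

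The largest shift, 12 points, is less than half the width of the first interval (26.0 − 1.0 = 25 points).

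**6. Could it happen at all?** The chance of at least one whole-intervention failure among 25 is 1 − (1 − p)^25: 40%, 72% or 93% for assumed per-patient rates p of 2%, 5% or 10%. Not all such patients would be in the Safety population.

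**The case against.** The strongest objection is that the decisive document is missing. SAP section 3 summarises the investigation plan, and for AE recording SAP 3.1 refers to plan Section 8, which may require follow-up after withdrawal. The SAP is based on plan version 2.0; the synopsis comes from Rev3, does not mention the rule, and runs each patient to Visit 5. The sentence may also have been meant only to say that secondary performance endpoints cannot be assessed after a failure. All of this stands as a reason to say that AEs may go unrecorded, not that they are lost. It does not rescue the sentence: if Section 8 requires follow-up or Rev3 dropped the rule, the SAP contradicts the plan.

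Other points stand in part:
- Visits 3 to 5 are routine, so clinical care continues. What is at risk is recording in the CRF, and a reader who infers that nobody examined these patients goes too far.
- SAP 5.5.1 reports missing counts and percentages of non-missing values. It does not clearly settle the AE denominator for a patient observed on one day and then withdrawn.
- SAP 6.1 plans disposition by population and visit, and Tables 1.4 and 1.5 with Listings 1.1, 1.4, 1.5 and 3.1 would let a reader find these patients. However, both tables are for the Screened population, and none of the planned tables isolates Safety patients without later AE follow-up.
- Safety is secondary and descriptive, with no threshold or comparator, so no planned decision rule would change.

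**Conclusion.** The point holds in conditional form. Followed as written, SAP 3.2.1 allows AEs after the intervention day to go unrecorded in patients who remain in the Safety denominator, and the bias has one direction: downward. The expected shortfall is 0 to 2.4 percentage points, assuming 25 Safety patients, 0 to 3 such failures, and a 5 to 20% chance of a first later event in each. It is zero if no such failure occurs.

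A reader might infer more than this. The documents do not show that any AE was lost, because neither plan Section 8 nor Rev3 is available. They do not support the view that intervention-day AEs are discarded, although the sentence taken literally would exclude them. Nor do they put every technical failure in the Safety population, since that needs at least one assisted needle. The 20.0% bound requires three whole-intervention failures, all with a later first event; it is a limit and not a forecast. The sentence should be corrected because the conflict is real and cheap to remove, not because a large distortion has been shown.

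**What to change.** 1. In SAP 3.2.1, and in the investigation plan if it still has the rule, state that a technical failure of the whole intervention ends performance follow-up only, and that AEs are recorded to at least the routine Visit 3 and analysed in the Safety population. If Rev3 dropped the rule, delete the sentence. The plan has to carry this change where the rule persists, because the SAP alone cannot create data collection.
2. In Table 4.2, give the number of Safety patients without AE follow-up after the intervention day. For any already withdrawn, show the overall AE rate twice: with them counted as event-free and as having an event.
3. Optionally, add technical failure of the whole intervention as an end-of-study reason in Table 1.5.

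The cost is one sentence in the SAP, a matching line in the plan if needed, two rows in Table 4.2, and a little more AE data collection at a visit that is already routine. Patients already withdrawn may have to consent again. SAP 5.1 planned the last patient's completion for Q1 2024, so the gain may now be limited to item 2, which needs no new data.
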